5.2.1.6 Timing of Dose Administration

Trial treatment should be administered on Day 1 of each cycle after all procedures/assessments have been completed as detailed on the Schedule of Assessments (Section 6.0). Trial treatment may be administered up to 3 days before or after the scheduled Day 1 of each cycle due to administrative reasons.

All trial treatments will be administered on an outpatient basis.

Pembrolizumab 200 mg will be administered as a 30 minute IV infusion every 3 weeks. Sites should make every effort to target infusion timing to be as close to 30 minutes as possible. However, given the variability of infusion pumps from site to site, a window of -5 minutes and +10 minutes is permitted (i.e. infusion time is 30 minutes: -5 min/+10 min).

The package insert contains specific instructions for the preparation of the pembrolizumab infusion fluid and administration of infusion solution.

Patients should store vorinostat capsules at room temperature, 15 to 30 °C (59 to 86 °F). Do not store above 30°C. Avoid exposure to excessive moisture. Vorinostat capsules must be administered whole. Administer doses of vorinostat with food if possible. Vorinostat capsule should be administered according to the package insert.

5.2.2 Trial Blinding/Masking

This is an open-label trial; therefore, the Sponsor, investigator and subject will know the treatment administered.

5.3 Concomitant Medications/Vaccinations (allowed & prohibited)

Medications or vaccinations specifically prohibited in the exclusion criteria are not allowed during the ongoing trial. If there is a clinical indication for one of these or other medications or vaccinations specifically prohibited during the trial, discontinuation from trial therapy or vaccination may be required. The investigator should discuss any questions regarding this with the Sponsor who will discuss this with the Merck Clinical team. The final decision on any supportive therapy or vaccination rests with the investigator and/or the subject's primary physician.

5.3.1 Acceptable Concomitant Medications

All treatments that the investigator considers necessary for a subject's welfare may be administered at the discretion of the investigator in keeping with the community standards of medical care. All concomitant medication will be recorded on the case report form (CRF) including all prescription, over-the-counter (OTC), herbal supplements, and IV medications and fluids. If changes occur during the trial period, documentation of drug dosage, frequency, route, and date may also be included on the CRF.

All concomitant medications received within 28 days before written informed consent and 30 days after the treatment discontinuation should be recorded. Concomitant medications

administered after 30 days after treatment discontinuation should be recorded for SAEs and ECIs as defined in Section 7.2.

5.3.2 Prohibited Concomitant Medications

Subjects are prohibited from receiving the following therapies during the Screening and Treatment Phase (including retreatment for post-complete response relapse) of this trial:

- Antineoplastic systemic chemotherapy or biological therapy
- Immunotherapy not specified in this protocol
- Chemotherapy not specified in this protocol
- Investigational agents other than pembrolizumab and vorinostat
- Radiation therapy
 - Note: Radiation therapy to a symptomatic solitary lesion or to the brain may be allowed at the investigator's discretion with written Sponsor approval.
- Live vaccines within 30 days prior to the first dose of trial treatment and while participating in the trial. Examples of live vaccines include, but are not limited to, the following: measles, mumps, rubella, varicella/zoster, yellow fever, rabies, Bacillus Calmette-Guérin, and typhoid vaccine.
- Systemic glucocorticoids for any purpose other than to modulate symptoms from an event of clinical interest of suspected immunologic etiology. The use of physiologic doses of corticosteroids may be approved after consultation with the Sponsor.

Subjects who, in the assessment by the investigator, require the use of any of the aforementioned treatments for clinical management should be removed from the trial. Subjects may receive other medications that the investigator deems to be medically necessary.

The Exclusion Criteria describes other medications which are prohibited in this trial.

There are no prohibited therapies during the Post-Treatment Follow-up Phase.

5.4 Rescue Medications & Supportive Care

Subjects should receive appropriate supportive care measures as deemed necessary by the treating investigator. Suggested supportive care measures for the management of adverse events with potential immunologic etiology for pembrolizumab are outlined in section 5.2.1.6 of the protocol and in section 6.4.1 of the Investigator's Brochure. Where appropriate, these guidelines include the use of oral or intravenous treatment with corticosteroids as well as additional anti-inflammatory agents if symptoms do not improve with administration of corticosteroids. Note that several courses of steroid tapering may be necessary as symptoms may worsen when the steroid dose is decreased. For each disorder, attempts should be made to rule out other causes such as metastatic disease or bacterial or viral infection, which might

require additional supportive care. The treatment guidelines are intended to be applied when the investigator determines the events to be related to pembrolizumab.

Note: if after the evaluation the event is determined not to be related, the investigator is instructed to follow the Investigator's Brochure but does not need to follow the treatment guidance (as outlined in the Investigator's Brochure). Refer to Section 5.2.1.6 for dose modifications.

It may be necessary to perform conditional procedures such as bronchoscopy, endoscopy, or skin photography as part of evaluation of the event. Suggested conditional procedures, as appropriate, can be found in the Investigator's Brochure.

5.5 Diet/Activity/Other Considerations

5.5.1 Diet

Subjects should maintain a normal diet unless modifications are required to manage an AE such as diarrhea, nausea or vomiting.

5.5.2 Contraception

Pembrolizumab and vorinostat may have adverse effects on a fetus in utero. Furthermore, it is not known if pembrolizumab or vorinostat have transient adverse effects on the composition of sperm. Non-pregnant, non-breast-feeding women may be enrolled if they are willing to use 2 methods of birth control or are considered highly unlikely to conceive. Highly unlikely to conceive is defined as 1) surgically sterilized (they have undergone a hysterectomy, bilateral tubal ligation, or bilateral oophorectomy), or 2) postmenopausal (a woman who is ≥ 45 years of age and has not had menses for greater than 1 year will be considered postmenopausal), or 3) not heterosexually active for the duration of the study. Acceptable methods of birth control include: abstinence, partner with previous vasectomy, placement of an intrauterine device (IUD), condom with spermicidal foam/gel/film/cream/suppository, diaphragm or cervical vault cap, or hormonal birth control (pills or injections). Subjects should start using birth control from written informed consent throughout the study period up to 120 days after the last dose of study therapy.

Male subjects without a previous vasectomy should agree to use an adequate method of contraception (i.e. abstinence, condom with spermicidal foam/gel/film/cream) starting with the first dose of study therapy through 120 days after the last dose of study therapy.

Subjects should be informed that taking the study medication may involve unknown risks to the fetus (unborn baby) if pregnancy were to occur during the study. In order to participate in the study they must adhere to the contraception requirement (described above) for the duration of the study and during the follow-up period defined in section 7.2.3-Pregnancy and Lactation. If there is any question that a subject will not reliably comply with the requirements for contraception, that subject should not be entered into the study.

5.5.3 Use in Pregnancy

If a subject inadvertently becomes pregnant while on treatment with pembrolizumab and/or vorinostat, the subject will immediately be removed from the study. The site will contact the subject at least monthly and document the subject's status until the pregnancy has been completed or terminated. The outcome of the pregnancy will be reported to the Sponsor and to Merck without delay and within 24 hours to the Sponsor and within 2 working days to Merck if the outcome is a serious adverse experience (e.g. death, abortion, congenital anomaly, or other disabling or life-threatening complication to the mother or newborn).

The study investigator will make every effort to obtain permission to follow the outcome of the pregnancy and report the condition of the fetus or newborn to the Sponsor. If a male subject impregnates his female partner the study personnel at the site must be informed immediately and the pregnancy reported to the Sponsor and to Merck and followed as described above and in Section 7.2.3.

5.5.4 Use in Nursing Women

It is unknown whether pembrolizumab or vorinostat are excreted in human milk. Since many drugs are excreted in human milk, and because of the potential for serious adverse reactions in the nursing infant, subjects who are breast-feeding are not eligible for enrollment.

5.6 Subject Withdrawal/Discontinuation Criteria

Subjects may withdraw consent at any time for any reason or be removed from the trial at the discretion of the investigator should any untoward effect occur. In addition, a subject may be withdrawn by the investigator or the Sponsor if enrollment into the trial is inappropriate, the trial plan is violated, or for administrative and/or other safety reasons. If a subject withdraws from the study, they will no longer receive study intervention or be followed at scheduled protocol visits. Specific details regarding discontinuation or withdrawal are provided in Section 7.1.4.1.

A subject must be discontinued from the trial for any of the following reasons:

- The subject or legal representative (such as a parent or legal guardian) withdraws consent.
- Confirmed radiographic disease progression (with the exception of pseudoprogression as described in Section 5.9)
- Any progression or recurrence of any malignancy, or any occurrence of another malignancy that requires active treatment
- Unacceptable adverse experiences as described in Section 5.2.1.7
- Intercurrent illness that prevents further administration of treatment
- Investigator's decision to withdraw the subject
- The subject has a confirmed positive serum pregnancy test
- Noncompliance with trial treatment or procedure requirements
- The subject is lost to follow-up
- Completed 24 months of uninterrupted treatment with pembrolizumab or 35 administrations of study medication, whichever is later.

Note: 24 months of study medication is calculated from the date of first dose. Subjects who stop pembrolizumab after 24 months may be eligible for up to one year of additional study treatment if they progress after stopping study treatment provided they meet the requirements detailed in Section 7.1.6.4

- Administrative reasons

The End of Treatment and Follow-up visit procedures are listed in Section 6 (Schedule of Assessments) and Section 7.1.6 (Follow-up Requirements). After the end of treatment, each subject will be followed for 30 days for adverse event monitoring (serious adverse events will be collected for 90 days after the end of treatment as described in Section 7.2). Subjects who discontinue for reasons other than progressive disease will have post-treatment follow-up for disease status until disease progression, initiating a non-study cancer treatment, withdrawing consent or becoming lost to follow-up. After documented disease progression, each subject will be followed by telephone for overall survival until death, withdrawal of consent, or the end of the study, whichever occurs first.

5.7 Discontinuation of Study Therapy after CR

Discontinuation of treatment may be considered for subjects who have attained a confirmed CR that have been treated for at least 24 weeks with combination vorinostat and pembrolizumab and had at least two treatments with vorinostat and pembrolizumab beyond the date when the initial CR was declared. Subjects who then experience radiographic disease progression may be eligible for up to one year of additional treatment with vorinostat and pembrolizumab via the Retreatment Phase at the discretion of the investigator if no cancer treatment was administered since the last dose of vorinostat and pembrolizumab, the subject meets the safety parameters listed in the Inclusion/Exclusion criteria, and the trial is open. Subjects will resume therapy at the same dose and schedule at the time of initial discontinuation. Additional details are provided in Section 7.1.6.4.

5.8 Subject Replacement Strategy

Patients who do not complete the first cycle of combination therapy during the dose finding phase will be replaced. Patients who cannot complete Cycle 1 of the expansion phase for reasons unrelated to the study drug will also be replaced.

5.9 Pseudoprogression

For a clinically stable subject with first radiologic evidence of progressive disease (PD), it is at the discretion of the site investigator to continue treating the subject with pembrolizumab until PD is confirmed at least 6 weeks from the date of the first tumor imaging suggesting PD. If radiologic PD is confirmed by the subsequent tumor imaging the subject should be discontinued from treatment unless, in the opinion of the investigator, the subject is achieving a clinically meaningful benefit.

5.10 Clinical Criteria for Early Trial Termination

Early trial termination will be the result of the criteria specified below:

1. Quality or quantity of data recording is inaccurate or incomplete
2. Poor adherence to protocol and regulatory requirements
3. Incidence or severity of adverse drug reaction in this or other studies indicates a potential health hazard to subjects
4. Plans to modify or discontinue the development of the study drug

In the event of Merck decision to no longer supply study drug, ample notification will be provided so that appropriate adjustments to subject treatment can be made.

6.0 SCHEDULE OF ASSESSMENTS

Trial Period:	Screening Phase	Run-in Phase ¹³	Combination Phase								End of Treatment	Post-Treatment			
			1	2	3	4	To be repeated beyond 8 cycles					Safety Follow-up ²	Follow-up Visits ³	Survival Follow-up	
Treatment Cycle	Screening ¹ (Visit 1)	-2	-1	1	D 14				5	6	7	8			
Scheduling Window (Days):	-28 days to start of first cycle	± 3	± 3	± 3	± 3	± 3	± 3	± 3	± 3	± 3	± 3	± 3	30 days post discon ± 3	Per institutional guidelines	Every 6 months ± 30
Administrative Procedures															
Informed Consent	x														
Inclusion/Exclusion Criteria	x														
Demographics and Medical History	x														
Registration	x														
Prior and Concomitant Medication Review	x														
Trial Treatment Administration		x	x	x	x	x	x	x	x	x	x	x			
Post-study anticancer therapy status												x	x	x	
Survival Status														x	
Clinical Procedures/Assessments															
Review Adverse Events			x	x		x	x	x	x	x	x	x	x		
Full Physical Examination ⁴	x	x	x	x		x	x	x	x	x	x	x			
Drug Compliance Review			x		x	x	x	x	x	x	x	x			
Vital Signs, Weight and Height (Screening Only)	x	x	x	x		x	x	x	x	x	x	x			
ECOG Performance Status	x	x	x	x		x	x	x	x	x	x	x			
Laboratory Procedures/Assessments⁹															

Trial Period:	Screening Phase	Run-in Phase ¹³	Combination Phase								End of Treatment	Post-Treatment			
			1	2	3	4	To be repeated beyond 8 cycles					Safety Follow-up ²	Follow-up Visits ³	Survival Follow-up	
Treatment Cycle	Screening ¹ (Visit 1)	-2	-1	1	D 14				5	6	7	8			
Scheduling Window (Days):	-28 days to start of first cycle	± 3	± 3	± 3	± 3	± 3	± 3	± 3	± 3	± 3	± 3	± 3	30 days post discon ± 3	Per institutional guidelines	Every 6 months ± 30
Pregnancy Test – Urine or Serum β-HCG	x ⁵						x ⁵								
PT/INR and aPTT	x														
CBC with Differential	x	x	x	x	x	x	x	x	x	x	x	x			
Comprehensive Serum Chemistry Panel	x	x	x	x		x	x	x	x	x	x	x			
Urinalysis	x		x		x		x		x		x	x			
T3, FT4 and TSH	x		x		x		x		x		x	x			
HgbA1c ¹¹	x	x	x	x	x	x	x	x	x	x	x				
Prostate Specific Antigen Test			x		x		x		x		x	x			
Efficacy Measurements															
Tumor Imaging – CT ¹⁶	x						x ¹³			x ¹⁶			x ¹²		
Tumor Imaging - Bone Scan	x						x ^{12, 13}			x ^{12,16}			x ¹²		
Tumor Imaging - ⁶⁸ Ga-PSMA-11 PET Scan ¹⁷	x						x ¹⁷								
Tumor Biopsies/Archival Tissue Collection/Correlative Studies Blood															
Archival (when available), Newly Obtained Tissue Collection (optional) ⁷	x			x ¹⁵											
Correlative Studies Blood Collection	x	x ⁸	x	x	x	x	x	x	x	x	x ¹⁰				

Footnotes:

¹ Procedures completed prior to consenting that are a part of a subject's standard of care may be used if they fall within the 28 day window to start treatment. Screening procedures completed 7 days of C1D1 do not need to be repeated.

² If the subject discontinues treatment due to disease progression, a phone call to the patient can serve as the Safety Follow-up Visit if the End of Treatment Visit was done. If a subject initiates a new anti-cancer therapy within 30 days after the treatment discontinuation, the 30 day Safety Follow-up Visit must occur before the first dose of the new therapy. Once new anti-cancer therapy has been initiated the subject will move into Survival Follow-up.

³ Applies to subjects who discontinue trial treatment for a reason other than disease progression. Subjects should be assessed per institutional guidelines by radiologic imaging to monitor disease status. Every effort should be made to collect information regarding disease status until the start of new anti-neoplastic therapy, disease progression, death, end of the study or if the subject begins retreatment with pembrolizumab.

⁴ Full physical exams may also be done by the investigator or qualified designee throughout participation in the trial as clinically indicated.

⁵ Only if clinically indicated and must be completed \leq 7 days prior to the first dose of study medication

⁶ It is recommended that after 1 year, imaging should be done every 6 months \pm 2 weeks; however, institutional guidelines and investigator discretion may vary.

⁷ Whenever possible, archival tissue from a tumor lesion will be obtained at screening. However, patients will be given the option to consent to a biopsy during the screening phase in case archival tissue cannot be retrieved and a second biopsy on Cycle 1 Day 14 (- 3 days). Missed tissue collection will not be considered a protocol deviation for the purposes of this study, as tissue collection is an exploratory objective for this study.

⁸ Run-in Phase, Cycle -2 Days 1 and 14

⁹ Laboratory tests for screening or entry into the Retreatment Phase should be performed within 10 days prior to the first dose of treatment. After Cycle 1, pre-dose laboratory procedures can be conducted up to 72 hours prior to dosing. Results must be reviewed by the investigator or qualified designee and found to be acceptable prior to each dose of trial treatment.

¹⁰ When patients are taken off treatment and at the time of disease progression blood for correlative markers will be also obtained.

¹¹ HgbA1c only required for patients with diabetes mellitus at time of study entry.

¹² Only as clinically indicated (Cohort A and B). Standard of care after initial ⁶⁸Ga-PSMA-11 PET (Cohort C)

¹³ Imaging will be done prior to dosing on C3D1.

¹⁴ The run-in phase will only be done during the Dose Expansion Phase and may be waived at the investigator's discretion.

¹⁵ Window for second biopsy is -3 days not +/- 3 days as is the case for other procedures at this time point. Biopsy should occur approximately 2 hours following the most recent dose of vorinostat on cycle 1 day 14. To ensure that these samples are obtained at the correct time, patients are urged to take their vorinostat dose in the clinic on the day of on-treatment sample collection.

¹⁶ Imaging will be done every 3 cycles beginning cycle 6 throughout treatment.

¹⁷ Applicable to a subset of patients in Cohort C (prostate cancer) only, as determined by the Principal Investigator. The Ga-PSMA-11 PET scan should be completed at 12 weeks (C4D1)

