Once the RP2D is identified, the Dose Expansion Phase will be opened. During the Dose Expansion Phase, the study will have a run-in phase with sequential single-agents (Schema B) and then the combination phase (Schema A). The run-in phase may be waived at the investigator's discretion. The reason for the run-in phase during dose expansion is to obtain data on the immunomodulatory effects of vorinostat separately from pembrolizumab. Forty-five patients with prior treatments will be enrolled in three expansion cohorts: 15 anti-PD1 naive renal and urothelial patients, 15 anti-PD1 resistant renal and urothelial patients (defined as patients with transient clinical response or without clinical response to prior immune-checkpoint inhibition), and 15 patients with androgen-sensitive or castration-resistant prostate cancer. The prostate cohort has been added in an amendment during the Dose Expansion Phase, and therefore, will not be part of the Dose Finding Phase.

Anti-tumor activity will be assessed by radiological tumor assessments conducted at baseline, 12 weeks and every 6 weeks thereafter, using RECIST version 1.1 (see Section 14.3). RECIST 1.1 will be used for treatment decisions until first radiologic evidence of progressive disease (PD). Following the first evidence of radiologic PD, treatment decisions may be made by the adaption of RECIST 1.1, termed the immune-related response criteria (irRC) (see Section 14.6) to account for the tumor response patterns seen with pembrolizumab treatment (e.g. tumor flare).

[figure not shown]
1 Cycle = 3 weeks (21 days)

Schema B: Run-In Phase

The RP2D is the dose of pembrolizumab and vorinostat in combination chosen for further clinical development. Further experience in the Dose Expansion Cohort may result in a RP2D dose lower than the MTD.

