8.9 Efficacy Analysis

Responses will be tabulated and objective response (CR+PR) via RECIST 1.1 will be summarized with the point estimate and corresponding exact 95% confidence interval. For patients with prostate cancer PSA response ($\geq 50\%$ decline from baseline), PSA progression ($\geq 50\%$ increase from baseline/nadir) and bone lesions progression on ^{68}Ga -PSMA-11 PET or bone scans (≥ 2 lesions from baseline with confirmatory scans 6 weeks later showing ≥ 2 additional lesions) will be reported. Progression free and overall survival will be estimated using standard Kaplan-Meier curves. The median time-to-event for each endpoint will be estimated along with the corresponding 95% confidence interval. Similar descriptive analyses will be performed using irRC criteria. Endpoints such as quantitative characteristics of humoral immune response will be characterized by their mean and corresponding 95% confidence interval. No statistical comparisons are planned. Analyses will be done separately by each expansion cohort. Patients enrolled in the Dose Finding Phase will be excluded when estimating efficacy for the design of a future trial.

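### No PSA is scheduled before the first dose in the prostate cohort, and Section 8.9 does not define the baseline that its PSA endpoints use

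*Combined protocol and SAP*

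**What the plan says.** Section 8.9 sets two PSA endpoints ("For patients with prostate cancer PSA response" opens the sentence). Response is a "decline from baseline" of at least 50%. Progression is an "increase from baseline/nadir" of at least 50%. Neither Section 8.9 nor any other section says which PSA value is the baseline.

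Section 6.0 is the only place that schedules PSA, in the row "Prostate Specific Antigen Test". Its first mark is at Cycle -1. In the same table the row "Trial Treatment Administration" starts at Cycle -2.

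Section 2.1 puts a run-in of sequential single agents ahead of the combination in the Dose Expansion Phase, which includes the 15 prostate patients (Cohort C). It adds: "The run-in phase may be waived at the investigator's discretion".

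**The concern.** A percentage decline from baseline measures drug effect only if the baseline precedes the drug. A site that follows this schedule exactly has no such value. Section 8.1 says missing data are not imputed. The analyst must then either leave the man out of the PSA summary or use a value drawn on study drug. In the second case, men in one cohort would have reference values taken after different exposures: one run-in cycle for some, and about two weeks of the combination for others as the table reads. Which of these applies would depend on an investigator's decision to waive the run-in.

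Any PSA movement before the first draw, up or down, is absorbed into the reference, so the 50% rule becomes a different rule for different men. Section 8.4 intends the expansion cohorts to inform the next study, so the PSA response rate may be carried forward with this shift in it.

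**Working it through.** The plan states no figure that depends on PSA timing, so there is nothing to reproduce. The check has two parts.

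**1. Reading the schedule.** Each row below splits into 15 columns. The first five are:

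| Row | Screening | Cycle -2 | Cycle -1 | Cycle 1 | D 14 |
|---|---|---|---|---|---|
| Treatment | – | x | x | x | x |
| CBC | x | x | x | x | x |
| Chemistry | x | x | x | x | – |
| Urinalysis | x | – | x | – | x |
| Thyroid | x | – | x | – | x |
| PSA | – | – | x | – | x |

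Over all 15 columns, urinalysis and thyroid are marked in columns 1, 3, 5, 7, 9, 11 and 12. PSA is marked in 3, 5, 7, 9, 11 and 12. The only difference is the missing Screening mark. A column shift in reading the PDF would have moved the other marks too, so it does not explain the gap.

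- With the run-in, the first scheduled PSA is at Cycle -1, after Cycle -2 treatment.
- With the run-in waived, the Cycle 1 column is also blank. The first scheduled PSA is in the column headed D 14, after the combination has started.

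**Could another provision move a draw ahead of treatment?**

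- Pre-dose laboratory window (Section 7.1.3): up to 72 hours. Visit window: ±3 days. Cycle length: 21 days. Using both windows in full, the Cycle -1 draw falls no earlier than 21 - 3 - 3 = 15 days after the nominal start of Cycle -2. It remains on treatment.
- Footnote 1: standard-of-care procedures done within 28 days before treatment may be used. This permits a PSA but does not require one.
- Footnote 9: sets the timing of screening laboratory tests but does not add PSA to them.

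**2. Consequence for the 50% rule.** Let g be the fractional change in PSA between the pre-treatment value and the first scheduled draw. The documents give no g, so the range used here is an assumption for illustration. A 50% fall from the first scheduled draw equals a fall from the pre-treatment value of

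1 - 0.5 × (1 + g).

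| Assumed g | Equivalent fall from pre-treatment |
|---|---|
| -30% | 1 - 0.5 × 0.70 = 65% |
| -20% | 1 - 0.5 × 0.80 = 60% |
| 0 | 50% |
| +20% | 1 - 0.5 × 1.20 = 40% |
| +30% | 1 - 0.5 × 1.30 = 35% |

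For progression measured from that draw, the trigger is 1.5 × (1 + g) times the pre-treatment level. At g = +30% this is 1.95 times instead of 1.5 times. At g = -30% it is 1.05 times. If the rule is read as the lower of baseline and nadir, a fall before the first draw would count as a nadir under either definition of baseline. The definition then changes progression only when PSA has risen.

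**Size at n = 15.** One reclassified man moves the rate by 1/15 = 6.7 points. For example, 3/15 is 20.0% (exact 95% CI 4.3% to 48.1%) and 4/15 is 26.7% (7.8% to 55.1%).

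**The case against.** **Baseline may still be pre-treatment in practice.** A reader might infer that the plan makes the PSA baseline an on-treatment value. The documents do not say so. Section 8.9 does not tie baseline to the first scheduled draw, and in ordinary use baseline means before treatment. Footnote 1 allows standard-of-care results, Section 7.1.1.5.1 collects disease details, and Section 7.1 allows unscheduled procedures when clinically necessary. All of this stands. It limits the point to what is scheduled and defined, because none of these provisions requires a pre-dose PSA.

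**The extracted table is imperfect.** The biopsy that the footnotes place on Cycle 1 Day 14 sits in the Cycle 1 column. One column carries imaging that the footnotes place at both C3D1 and C4D1. If the PSA mark under D 14 really belongs to Cycle 1 Day 1, a man whose run-in is waived would have a pre-dose value, since the section on timing of dose administration puts Day 1 procedures before treatment. Blank physical-examination and vital-sign cells under D 14 favour Day 14, but this is not certain. The run-in case does not depend on it, because the first four columns agree across the header, treatment, CBC and chemistry rows.

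**PSA is not a named objective.** One might call PSA a main activity measure for this cohort. Section 3 does not support that: the primary objective names objective response rate and progression-free survival, and PSA appears in no objective. Section 8.9 only reports it, with no comparisons planned.

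**The run-in is optional,** so the number of men affected is unknown. This stands.

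**PSA is also absent from Table 5.** That adds little, because HgbA1c is scheduled and is missing from Table 5 as well.

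**Conclusion.** The point holds in limited form. The schedule contains no PSA before the first dose for men who have the run-in and, as the table reads, none for men whose run-in is waived. Section 8.9 leaves baseline undefined. Unless a standard-of-care value happens to exist, the reference is an on-treatment value that differs with the waiver.

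The effect is confined to the descriptive PSA response and PSA progression summaries in Cohort C. RECIST response and progression-free survival have baseline imaging. The 65% to 35% range rests on the assumed g of -30% to +30%. The 6.7 points per man rests on 15 evaluable men. How many would be reclassified cannot be estimated from the documents. The omission is worth correcting because it is cheap to fix and a missed pre-treatment sample cannot be drawn later.

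**What to change.** - Section 6.0: add a PSA mark at Screening for Cohort C.
- Section 8.9: define PSA baseline as the last value before the first dose of any study drug, meaning before Cycle -2, or before Cycle 1 if the run-in is waived.
- For men already enrolled, retrieve standard-of-care pre-treatment PSA values from records, and report how many men have none.
- Listing PSA in Table 5 is optional housekeeping.

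The cost is a minor amendment and one routine blood test in 15 men, taken at the existing screening draw.
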